11.2 Reference Allergens

Commercially available reference allergens may be used or the reference allergen syringes may be prepared and labeled by the Department of Occupational and Environmental Dermatology, Skåne University Hospital, Malmö, Sweden. The reference allergens will be stored in individual syringes under refrigeration at 2 - 8°C.

The Finn Chamber, polypropylene-coated, supplied by SmartPractice, will be used to apply the reference allergens. Reference allergens will be dispensed at the rate of 20 µl/chamber using a precision allergen dispenser.

Figure 10: Reference Allergen Preparation

Petrolatum allergens

◀ Apply a ribbon of substance across the diagonal of chamber

Petrolatum allergens may be dispensed 24 hours prior to application

Liquid allergens

◀ Add filter paper to chamber

Dispense liquid allergen to chamber ➔

Liquid allergens may not be dispensed until immediately prior to patch application

Instructions for precision allergen dispenser:

1. Fill metering chamber with allergen using syringe plunger.
2. Wipe excess from tip.
3. Dispense allergen to chamber by depressing precision allergen dispenser plunger.

- The Aluminum Dilution Series will be tested concurrently with
 - Aluminum chloride hexahydrate, 10 % w/w in petrolatum
 - Aluminum lactate, 12 % w/w in petrolatum
- The Copper Dilution Series will be tested concurrently with copper sulfate anhydrous, 2 % w/w in petrolatum
- The Manganese Dilution Series will be tested concurrently with manganese chloride tetrahydrate, 2 % w/w in petrolatum
- The Molybdenum Dilution Series will be tested concurrently with ammonium molybdate, 1% aqueous solution.
- The Tin Dilution Series will be tested concurrently with tin chloride dihydrate, 1% w/w in petrolatum
- The Titanium Dilution Series will be tested concurrently with
 - Ammonium titanium peroxy citrate, 17% w/w in petrolatum
 - Ammonium titanium lactate, 34% aqueous solution
 - Potassium titanium oxide oxalate, 22% w/w in petrolatum
 - Ammonium Titanium oxide oxalate 19% w/w in petrolatum
- The Vanadium Dilution Series will be tested concurrently with
 - Vanadium chloride, 1% w/w in petrolatum
 - Vanadium oxide sulfate, 1.5% w/w in petrolatum
- The Zinc Dilution Series will be tested concurrently with zinc chloride, 2% w/w in petrolatum

NOTES: 1) The common allergens (Panel 6) will not be tested against reference allergens. 2) Subjects enrolled in Germany will not be tested with the reference allergens

12.0 DATA ANALYSIS

12.1 Descriptive Statistics and Analysis

True disease status (allergic contact dermatitis to a specific allergen) is rarely definitively known. Patch test results, medical history, symptoms and provocation testing (if performed) are used to clinically diagnose disease status, and it is not uncommon to observe discordance among these diagnostic parameters. Moreover, symptoms and test results can change over time – presumably due to skin condition, decreased exposure or overall health. These factors contribute to the difficulty of assigning a positive disease status, i.e., sensitive status, to patients. In this clinical trial, subjects will be considered sensitive if they've had a past positive response even though they may not react to the reference allergen at the time of the study.

The frequency of ranked skin responses; positive (1+, 2+, 3+), negative, doubtful and irritant, will be calculated for each allergen dose (dilution series and reference) tested. The optimal allergen dose will be based on the following criteria:

- The lowest concentration of each dilution series allergen eliciting positive responses in a minimum of 15 subjects. Positive responses are defined as score of 1+, 2+ or 3+ during at least one reaction assessment visit. If a significant number of 3+ responses are elicited, the dose will be selected based on 1+ and 2+ responses.
- For all sites with the exception of Germany: Concordance will be measured using Cohen's kappa where less than 0% indicates no agreement, 0-20% indicates poor agreement, 20-40% indicates fair agreement, 40-60% indicates moderate agreement, 60-80% indicates good agreement and 80% or higher indicates very good agreement. Concordance will be measured using all subjects who are tested with each allergen and corresponding reference allergen.

Safety evaluations will be tabulated as follows:

- Frequency of tape and polyester chip induced irritation or allergic reactions at Visits 2 through 6 for the T.R.U.E. Test tape and polyester chips (Panels 1-6) and Finn Chamber tape (Reference allergen panels).
- Frequency of subject reported sensations of itching and/or burning for each allergen panel at patch removal.
- Frequency of positive (1+, 2+, 3+) skin reactions for each investigational and reference allergen dose at each post removal visit and overall.
- Frequency of negative, doubtful, irritant, late and persistent skin reactions for each investigational and reference allergen dose at each post removal visit (late and persistent reactions at visits 4, 5 and 6 only).
- Frequency of all adverse events. Documentation for all local and systemic adverse reactions classified by the investigator as possibly or definitely related to the study product (e.g., erythema, hyper-pigmentation, hypo-pigmentation, skin thinning or dermatitis flare) will include grade (mild, moderate or severe) and time point (clinic visit).

Statistical processing will be performed using SAS® software.

12.2 Sample Size and Power Calculations

A minimum of 15 subjects per dilution series allergen, who exhibit a positive skin response (score of 1+, +2 or 3+ during at least one reaction assessment visit) to the dilution series allergen and/or at least one of its corresponding reference allergens, is needed to complete the study.

Subjects with a past positive patch test response to at least one of the dilution series allergens will be tested with the allergen panel and corresponding reference allergen(s) to which they have had the previous response. Subjects with suspicion of metal contact allergy will be tested with all dilution series and reference allergens. All subjects will be tested with the excipient controls. The common allergens will be tested at the discretion of the investigator.

Past dose response study populations have included 20 adult subjects (per allergen) with a historical positive patch test to the corresponding reference allergen. In these studies, determination of the optimal test allergen dose was the lowest concentration eliciting a 1+, 2+ or 3+ positive reaction in 70-90% of subjects with the fewest number of 3+ reactions; therefore a minimum of 14 subjects with positive reactions was needed to determine optimal test allergen dose.

Due to the fact that not all of the metals being tested on this study have a large database of patients with past patch-test positive reactions, the inclusion criteria was modified to include subjects with a suspicion of metal allergy, in addition to those with a historical positive patch test. Because it is anticipated that not all subjects will test positive, the study will conclude when a total of 400 subjects have been tested.

The option of further testing may be considered for any allergen that elicits a minimum of 8 positive responses. In such a case, the protocol will be amended

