7.1 Primary Endpoint

Determination of optimal test allergen dose as:

- The lowest concentration of each dilution series allergen eliciting positive responses in a minimum of 15 subjects. Positive responses are defined as score of 1+, 2+ or 3+ during at least one reaction assessment visit. If a significant number of 3+ responses are elicited, the dose will be selected based on 1+ and 2+ responses.
- For all sites with the exception of Germany: Concordance will be measured using Cohen's kappa where less than 0% indicates no agreement, 0-20% indicates poor agreement, 20-40% indicates fair agreement, 40-60% indicates moderate agreement, 60-80% indicates good agreement and 80% or higher indicates very good agreement. Concordance will be measured using all subjects who are tested with each allergen and corresponding reference allergen.

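### The 15 positive subjects needed to complete the study are not counted on the same event as the 15 the dose rule requires, so an allergen can meet its quota with no selectable dose

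*Protocol*

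**What the plan says.** Two rules use the number 15.

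- **Completion.** Protocol 12.2 asks for this: "A minimum of 15 subjects per dilution series allergen, who exhibit a positive skin response", where the response may be "to the dilution series allergen and/or at least one of its corresponding reference allergens, is needed to complete the study". No dose is named. Protocol 4.9 and 9.0 and SAP 3.3 give the same count.
- **Dose selection.** Protocol 7.1 defines the optimal dose as "The lowest concentration of each dilution series allergen eliciting positive responses in a minimum of 15 subjects". Protocol 12.1 and SAP 4.1 and 6.1 repeat this, with a clause that can only shrink the count at a dose: "If a significant number of 3+ responses are elicited, the dose will be selected based on 1+ and 2+ responses".

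The support offered for the size is a precedent: "Past dose response study populations have included 20 adult subjects (per allergen) with a historical positive patch test". Protocol 12.2 gives the criterion used in those studies: "lowest concentration eliciting a 1+, 2+ or 3+ positive reaction in 70-90% of subjects with the fewest number of 3+ reactions". From this the plan derives 14 positives as the smallest number those studies required.

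Protocol 12.2 and SAP 3.3 end the study at 400 subjects tested, and Protocol 4.10 adds that this holds even if the quota is not met. Further testing may be considered, by amendment, "for any allergen that elicits a minimum of 8 positive responses".

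**The concern.** A subject positive only on the reference patch counts toward completion but is negative at every investigational dose. A subject who reacts only at the highest dose counts toward completion but not toward any lower dose. The number positive at one dose can never exceed the number counted for completion and will usually be smaller. Using 15 for both leaves no margin between them, whereas the cited precedent had one: 20 subjects, with 14 needed at the dose.

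The plan presents 15 as what the study needs, yet reaching it does not deliver the first part of the primary endpoint. Neither document says what is reported for an allergen with 15 or more counted reactors and no dose reaching 15.

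The unit is also loose. Aluminum, vanadium and titanium carry two, two and four compounds, and the wording about at least one of several reference allergens suggests that the count is per metal. Neither document defines this.

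**Working it through.** **Inputs from the documents.** Quota 15 (12.2). Dose threshold 15 (7.1). Precedent of 20 subjects, 70-90% positive at the chosen dose, minimum 14 (12.2). Cap 400 (12.2, 4.10). No alpha, power, expected share of reactors or dropout is given for the 15 or the 400, so neither figure can be re-derived.

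**Assumptions.** p is the share of counted reactors who are positive at a given dose. The range 0.70-0.90 is borrowed from the precedent, where it describes historical positives. Subjects are treated as independent, and one dose is examined.

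**1. The plan's own figure.** 0.70 × 20 = 14, which reproduces. The precedent's chance of at least 14 positives among 20 was 0.61, 0.91 and 0.998 at p = 0.70, 0.80 and 0.90.

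**2. Exactly 15 counted reactors.** The dose qualifies only if all 15 react to it, with probability p^15. For an 80% chance, p must be at least 0.80^(1/15) = 0.985. One reference-only subject among the 15 makes the probability 0.

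**3. Reactors needed.** Smallest n with P(Bin(n, p) ≥ 15) ≥ 0.80.

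| p | Expected at the dose, 15p | p^15 | n for 80% (probability reached) |
|---|---|---|---|
| 0.90 | 13.5 | 0.206 | 18 (0.902) |
| 0.80 | 12.0 | 0.035 | 20 (0.804) |
| 0.70 | 10.5 | 0.005 | 24 (0.847) |

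If 20% of counted reactors were reference-only (assumption), p is multiplied by 0.8, and n becomes 23 at p = 0.90 and 30 at p = 0.70.

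**4. Testing to the cap.** Let q be the share of the 400 who are counted reactors (assumption). The quota is met with P(Bin(400, q) ≥ 15), and one dose reaches 15 with P(Bin(400, q·p) ≥ 15). At q = 0.05 the expected numbers are 400 × 0.05 = 20 reactors, and 20 × 0.90 = 18 or 20 × 0.70 = 14 at the dose.

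| q | Quota met | 15 at one dose, p = 0.90 | 15 at one dose, p = 0.70 |
|---|---|---|---|
| 0.04 | 0.64 | 0.47 | 0.16 |
| 0.05 | 0.90 | 0.80 | 0.43 |
| 0.06 | 0.98 | 0.95 | 0.71 |
| 0.08 | 1.00 | 1.00 | 0.96 |

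This takes all 400 as tested with the allergen. Subjects enrolled on a past positive may wear only the relevant panel, so the true number can be lower.

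**5. What can be counted blind.** Protocol 11.1 keeps the position key confidential until all study procedures are complete. Panels 1, 4 and 5 mix compounds and doses across positions, so neither is visible during recruitment. The metal is visible: Panels 1, 4 and 5 carry one metal each, and Panels 2 and 3 give each metal its own positions. Reference patches are in separate chambers.

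**The case against.** Four points on the other side have force.

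- **No stop at 15.** A reader might infer that recruitment for an allergen closes at 15 and that 0.21, 0.035 and 0.005 are the trial's chances of selecting a dose. The documents do not support that. Fifteen is a minimum, completion refers to the study as a whole, and the explicit stop is 400 tested. Commoner allergens may well pass 15. Those probabilities describe the boundary case; the cap figures describe a full run, and there the gap is smaller but present.
- **The 70-90% is borrowed.** It is the share of historical positives reacting at the chosen dose, not a share of current reactors to series or reference. The rule may be met at any dose, including the highest, where the share could be larger. Reference-only reactors pull it down. The net direction is unknown.
- **The endpoint event cannot be counted during recruitment.** A reader might conclude that completion should simply require 15 positives at one dose of one compound. Under the blind in 11.1 that would need early release of the key or an independent unblinded counter. A broad count is what the sites can keep.
- **Reference-only reactors are informative.** The other part of the primary endpoint is kappa against the reference, and it needs discordant results. Including them in a quota is defensible.

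Two further readings go too far. The matching dose labels of the two vanadium salts might suggest adding the salts to reach 15, but the tables in 11.1 list each salt as its own allergen, and SAP 6.1 scores by the allergen dose at each position. One titanium reactor, wearing 12 investigational patches, might seem able to supply all 8 responses for further testing, but 4.10 expresses the quota in subjects, and the option is discretionary and needs an amendment. Both call only for a stated unit.

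None of this removes the mismatch or supplies the missing outcome rule.

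**Conclusion.** The point holds in this limited form: the stated requirement and the dose rule count different events, and meeting the first does not secure the second. It is present in the current protocol and carried unchanged into the SAP. It does not depend on whether the quota is per metal or per salt, because the any-dose and reference-only elements remain either way.

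The size depends on assumptions. In a full run with 5% reactors, the shortfall against the quota probability is 0.90 − 0.80 = 0.10 at a 90% share and 0.90 − 0.43 = 0.47 at a 70% share. It is near zero at 8% reactors with a 90% share, and it widens as reactors become rarer or more of them react to the reference only. The documents give no figure for either. Because it concerns the primary endpoint and is cheap to put right, it should be corrected.

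**What to change.** - In Protocol 4.9, 9.0 and 12.2 and SAP 3.3, describe 15 as a blinded recruitment quota that does not by itself deliver the dose rule. State whether it is per metal or per compound.
- Beside it, give the reactors needed for an 80% chance of 15 at one dose (18, 20 or 24 at shares of 90%, 80% or 70%), or the probabilities above, with the shares labelled as assumptions.
- Tally reference-only reactors separately from subjects positive on an investigational patch. This can be done blind at metal level.
- In SAP 6.1, apply the count per compound and per dose, only after the randomization key is released. State that an allergen meeting the quota with no dose reaching 15 is reported as having no optimal dose determined.
- State that the threshold of 8 for further testing counts subjects.

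The cost is wording and one extra tally. The cap of 400 and the blind are unchanged. The SAP is to be final before database lock, so its parts can still be added if recruitment has closed. The downside is that the stated size looks less favourable, and some allergens may be reported with no dose selected.

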12.3 Data Monitoring and Quality Assurance

The study will be performed according to ICH harmonized Tripartite Guidelines for Good Clinical Practice, national legislation and SmartPractice internal SOPs for Clinical Studies. Study sites will be visited at least once prior to initiation of the study, at approximately 8-12 week intervals or as needed during the study and at the conclusion of the study. The sponsor will perform all monitoring.

Subject data will be recorded in data collection forms. These data will be entered into SAS, for subsequent analysis, and proofread for entry errors. Statistical analysis will be performed according to Good Clinical Practice and ICH guidelines using SAS software per the respective analytical parameters.

13.0 ADVERSE EVENTS

13.1 Adverse Event Definitions

- **Adverse Event (AE):** Any untoward medical occurrence associated with the use of a drug in humans, whether or not considered drug related
- **Adverse Reaction or Adverse Drug Reaction (ADR):** Any adverse event caused by a drug.
- **Life-threatening Adverse Event or Life-threatening Suspected Adverse Reaction:** An adverse event or suspected adverse reaction is considered 'life-threatening' if, in the view of either the investigator or the sponsor, its occurrence places the subject at immediate risk of death. This does not include an adverse event or suspected adverse reaction that had it occurred in a more severe form, might have caused death.
- **Serious Adverse Event (SAE) or Serious Suspected Adverse Reaction (SSAR):** An AE or SAR is considered serious if, in the view of either the investigator or sponsor it results in any of the following outcomes:
 - Death
 - A life-threatening adverse event
 - Inpatient hospitalization or the prolongation of existing hospitalization
 - A persistent or significant incapacity or substantial disruption of the ability to conduct normal life functions
 - Is a congenital anomaly/birth defect

Important medical events that may not result in death, be life-threatening or require hospitalization may be considered serious when, based upon appropriate medical judgment, they may jeopardize the subject and may require medical or surgical intervention to prevent one of the outcomes listed in this definition.
- **Suspected Adverse Reaction (SAR):** Any adverse event for which there is a reasonable possibility that the drug caused the adverse event. 'Reasonable possibility' means there is evidence to suggest a causal relationship between the drug and the adverse event. 'Suspected adverse reaction' implies a lesser degree of certainty about causality than adverse reaction.
- **Suspected Unexpected Serious Adverse Reactions (SUSAR)**
An adverse reaction that is both unexpected (not consistent with the applicable product information) and also meets the definition of a Serious Adverse Event/Reaction.
- **Unexpected Adverse Event (UAE) or Unexpected Suspected Adverse Reaction (USAR):**
An AE or SAR is considered 'unexpected' if it is
 - not listed in the investigator brochure
 - not listed at the observed specificity
 - not consistent with the risk information described in the general investigational plan or in the current application.

13.2 Adverse Event Reporting Period

The adverse event-reporting period for each study subject begins at panel application and ends with the Day 21 visit. All adverse events that occur in study subjects during the adverse event-

reporting period specified in the protocol must be reported. In addition, any known adverse event that occurs in a study subject after Day 21 that the investigator determines as possibly related to the investigational product must also be reported as an adverse event.

13.3 Serious Adverse Events

Serious adverse events must be documented and reported to the sponsor, SmartPractice, within 24 hours of the investigator's learning/awareness of the event. This initial report must be followed by submission of more detailed adverse event within 5 working days.

Serious, unexpected reactions that are not fatal or life-threatening will be filed no later than 15 calendar days after first knowledge by the sponsor.

Determination of expectedness will be based on the contents of the Investigators Brochure.

13.4 Suspected Unexpected Serious Adverse Reactions (SUSARs)

An adverse event will be reported as a **SUSAR if the following three criteria** are met:

1. The event is serious, that is to say irrespective of the dose the event:
 - is fatal, and/or
 - is life-threatening for the subject, and/or;
 - makes hospital admission or an extension of the admission necessary, and/or
 - causes persistent or significant invalidity or work disability, and/or
 - manifests itself in a congenital abnormality or malformation
2. There is a certain degree of probability that the event is harmful, and an undesirable reaction to the experimental product being research, regardless of the administered dosage. In other words, there is an adverse reaction.
3. The adverse reaction is unexpected. That is to say, the nature and severity of the adverse reaction are not in agreement with the product information as recorded in the Investigator's Brochure.

Fatal or life-threatening unexpected ADRs will be reported to all regulatory agencies and IRB/Ethics Committees by telephone, facsimile or in writing as soon as possible but no later than 7 calendar days after first knowledge by the sponsor followed by as complete a report as possible within 8 additional calendar days.

Deciding whether the adverse event meets the definition of a suspected adverse reaction is usually the most difficult determination. The sponsor will evaluate the available information and decide whether there is a reasonable possibility that the drug caused the adverse event and, therefore, that the event meets the definition of a suspected adverse reaction. The suspected adverse reaction must then be reported expeditiously in a safety report if it also meets the definitions of serious and unexpected.

The only response to a dermatological patch product that would trigger a SUSAR report would be anaphylactic reaction. There may be other reactions which would be categorized as SUSARs that are unknown at this time.

13.5 Severity

The investigator will provide an assessment of the severity of each adverse event by recording a severity rating on the appropriate AE reporting page of the subject's data collection form. (Severity, which is a description of the intensity of manifestation of the AE, is distinct from seriousness, which implies a subject outcome or AE-required treatment measure associated with a threat to life or functionality.) Severity will be assessed according to the following scale:

Mild: Minimal symptoms / annoying / minimal discomfort. Does not interfere with subject's usual function

Moderate: Definite discomfort / requires medication for relief. Interferes to some extent with subject's usual function

Severe: Symptoms interfere significantly with subject's usual function (daily activity / sleep).

The Investigator must supervise topical treatment of subject dermatitis and patch test responses.

